### Exposure and Outcome Definitions

#### Aim 1 exposure

- Allocation arm
  - Intervention block group for all eligible participants during that “on block” (regardless of actual monitoring receipt i.e., intention-to-treat).

#### Aim 1

##### Primary outcomes

- Composite of severe maternal outcome – one or more of the following outcomes represented in Table 1

**Table 1: Severe Maternal Outcomes**

Outcome	Definition/Measurement
Death	Mortality occurring at any time point after delivery and prior to discharge
Clinical based near-miss criteria	
Acute cyanosis	Blue or purple coloration of the skin or mucous membranes due to low oxygen saturation
Gasping	Terminal respiratory pattern, the breath is convulsively and audibly caught.
Oliguria	Urinary output < 30 ml/hour for 4 hours or < 400 ml/24 hours non-responsive to fluids/diuretics
Failure to form clots	Bedside clotting test or absence of clotting from the IV site after 7 minutes
Prolonged unconsciousness	Complete or near-complete lack of responsiveness to external stimuli
Cardiac arrest	Sudden absence of pulse and loss of consciousness
Stroke	Neurological deficit of cerebrovascular cause persisting $\geq 24$ hours
Uncontrollable fits	Refractory, persistent convulsions or status epilepticus
Total paralysis	Complete or partial paralysis of both sides of the body
Jaundice in the presence of pre-eclampsia	BP > 140/90 with proteinuria ( $> 1$ + dipstick in $\geq 2$ samples) and jaundice
Laboratory-based near miss criteria	
Acute severe azotemia	Creatinine $> 300$ mmol/l or $> 3.5$ mg/dl
Severe acute hyperbilirubinemia	Bilirubin $> 100$ $\mu$ mol/l or $> 6.0$ mg/dl.
Severe acute thrombocytopenia	$< 50\,000$ platelets/ml
Management-based near-miss criteria	
Use of continuous vasoactive drugs	Uninterrupted infusion of dopamine, epinephrine, or norepinephrine
Hysterectomy	Surgical removal of the uterus following infection or hemorrhage
Massive transfusion	Transfusion of $\geq 5$ units of blood
Intubation and ventilation not related to anaesthesia	Placement of an endotracheal tube or ventilation for $> 60$ minutes purposes other than anaesthesia
Dialysis for acute renal failure**	
Cardiopulmonary resuscitation	Emergency procedures including chest compressions and lung ventilation

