7. To evaluate if motion in the early post-operative period is related to functionality, mobility and wellness during recovery from cesarean delivery and how recovery relates to financial risks after cesarean delivery.

Methodology

Setting: The research will be carried out in the Department of OB/GYN MRRH in Mbarara, Uganda. This facility is the primary referral hospital in southwest Uganda. It performs ~ 10,000 deliveries per year (~ 30/day), has a maternal mortality ratio of 460 per 100,000 live births (~50-60 deaths per year)

and a cesarean delivery rate of 40%. All women delivered by cesarean are followed and monitored by postgraduate doctors with assistance from midwives. In this facility, postgraduate doctors complete medical training including a two-year internship and practice independently for several years prior to postgraduate training in OB/GYN. Consultant/Specialist OB/GYN supervisors oversee clinical care from home or in-hospital depending on clinical acuity. There are currently 13 consultants/specialists, 39 postgraduate doctors in the institution, and 40 midwives with clinical privileges in the department. The physician to patient ratio ranges from 1:8 during the day to 1:25 during the night and weekends.

Study Population:

The following types of participants will be recruited for study purposes:

- 1) Clinicians: Consultants/Specialists and nurse/midwives with clinical duty on the maternity ward at MRRH during the study period.
- 2) Peripartum women delivered by emergency cesarean during the study period.

Study Intervention:

The intervention in this study is the use of a wireless monitor to perform physiologic monitoring of women undergoing emergency cesarean delivery for the first 24 hours after completion of the cesarean.

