On average approximately 8-10 emergency cesarean deliveries are performed at MRRH daily. Thus, in a two week block we estimate ~ 112 emergency cesareans performed. We plan to capture all women delivered by emergency cesarean during an intervention block thus minimizing the risk of selection bias based on the severity level. Assuming 85% of women consent to participation (conservative estimate based on >90% recruitment in prior studies)^{5,74,75}, this yields an estimated 95 women per block. Over 12 months of enrollment, we will therefore have 13 intervention blocks and 13 control blocks. This yields an estimated 1,235 women in the intervention group and 1,235 in the control group. Assuming an intraclass correlation coefficient of 0.01, the effective sample size after taking account of clustering is 633 per group. This will allow us to detect a difference of 5.7% in the SMO rate between the two study arms, with a two-sided significance level of 0.05, and 80% power, assuming a baseline rate of SMO of 13% ^{71,73}

Risk/Discomforts and protections

Clinicians:

- Risk of false alerts, alert fatigue: Clinicians will be asked to hold a mobile phone and respond to alerts. It is possible that alerts of physiologic sign abnormalities may not correspond to a developing or established clinical abnormality and in responding to the alert clinicians may become fatigued from alerts. Study investigators will monitor for this occurrence and the impact on clinician performance and duties and adjust study protocols as necessary
- Risk of diversion and interruptions to work on other patients: Alerts sent to clinicians may also prompt them to perform additional exams or clinical procedures that may or may not be beneficial to the patients from which alerts were received. This may divert attention or human resource away from other clinical needs. We will monitor for any diversions resulting in substandard clinical care. If these occur we will consider protocol modifications. Any safety concerns or adverse events arising because of false alerts or diversions will be communicated to the IRB within 10 days.

Peripartum women:

- Theoretical risk of exposure to radio emissions from Wi-Fi from the biosensor: There is a theoretical risk of exposure to Wi-Fi signals from the biosensor worn by women participating in

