#### Protocol Deviations

Protocol deviations will be summarized in frequency tables

**Aim 1: To estimate the clinical effectiveness of wireless physiologic monitoring of women in the first 24 hours after cesarean delivery**

**Exposure** Intervention arm

**Primary outcome** Severe Maternal Outcome

**Endpoint** Discharge from hospital

**Descriptive statistics:** Proportion of women with one or more SMO, overall and by arm.

**Inferential statistics:** SMO will be statistically compared by arm using a Poisson model.

An intention to treat approach will be used to assess effectiveness. Thus, all women eligible for monitoring during an intervention arm including those who 1) declined consent 2) were missed from screening 3) were screened and not enrolled 4) enrolled but did not receive the intervention will be included in the intervention. The event rate for the primary and secondary outcomes will be calculated during the intervention and control time periods on all eligible women during those time periods. While intervention allocation was at the level of the two-week time period, the analysis will be at the individual patient level adjusting for clustering of observations within time periods. Using a logistic regression mixed effects model, with random effects to account for time block, we will compare the rate primary outcome between the intervention and control time periods.

Exploratory analyses will be used to determine if the intervention has a more significant effect in certain sub- groups of women (e.g. women <35, or women with more education). The interaction between study arm and comorbidities (i.e., HIV, hypertension, pulmonary, cardiac or kidney disease, malaria) will also be tested in logistic regression models. Subgroup effects will be reported if there is strong evidence of heterogeneity of intervention effect.

**Commented [BAA3]:** Intervention time periods will include women who  
-Declined consent  
-Were missed from screening  
-Were screened and unable to enroll  
-Enrolled but did not get the “full intervention”  
-Screened and enrolled – deceased before monitoring  
-Women ineligible due to language but those women will not be known in the control group.

**Commented [BAA4]:** Random effects for week using a mixed effects model  
Vs GEE where you put in clustering or correlation

**Commented [BAA5]:** Account for missing data in control period  
- impute for variables that are available and are independent for the intervention  

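### The near-miss components of the primary composite have no start of window, so events before or during the cesarean can count although monitoring begins only after surgery

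*SAP*

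**What the plan says.** The intervention is wireless monitoring "for the first 24 hours after completion of the cesarean" (Protocol, Study Intervention). Under Study Procedures, the sensor is placed once the operation is finished.

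The SAP defines the primary outcome as one or more rows of its Table 1. That table has 20 rows: death and 19 near-miss criteria. Death is "Mortality occurring at any time point after delivery and prior to discharge", which gives it a start and an end. The near-miss rows give no start. Hysterectomy, for example, is "Surgical removal of the uterus following infection or hemorrhage". Protocol Table 2 follows the same pattern, with two further near-miss rows (abnormal respiratory rate and shock).

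The SAP's Aim 1 analysis sets the end of the window at hospital discharge and includes all eligible women in each block. Under the Protocol's Study Procedures, chart review looks for any documented severe maternal outcome (SMO), without reference to when it began. Women admitted to ICU directly after delivery are excluded (Protocol, Subject Selection).

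On size, the Protocol says: "This will allow us to detect a difference of 5.7% in the SMO rate between the two study arms". It assumes a 13% baseline rate and does not say which time window that rate covers.

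**The concern.** Several near-miss components can occur before or during an emergency cesarean: hysterectomy at the operation, transfusion of five or more units in theatre, clotting failure, refractory convulsions, cardiac arrest. The Protocol also provides for enrolling women who are unconscious when consent would be sought, which is before surgery. Prolonged unconsciousness is a primary component and has no stated duration, so such a woman could meet the endpoint before a sensor is placed.

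Monitoring that starts after surgery cannot change these events in either arm. Counting them adds the same background to both arms and shrinks the difference the trial can see. A null result would then be hard to read: it could mean that monitoring does not work, or that too many of the counted events were already settled when it began.

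**Working it through.** **Inputs from the documents.** Baseline SMO 13%, difference 5.7 points, two-sided 0.05, 80% power, ICC 0.01, 95 women per block, 13 blocks and 1,235 women per arm, effective size 633 per arm (Protocol, Sample Size). The SAP (Study size and Power) gives 1,266 women, 633 per arm, as enrolled.

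**Input assumed.** f, the share of SMOs with onset before the end of surgery. The documents do not give it; 10%, 25% and 40% are used.

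**Formula.** With d = p1 − p2 and p̄ the mean of the two rates, power = Φ{[d√n − 1.96√(2p̄(1−p̄))] / √(p1(1−p1) + p2(1−p2))}.

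**Step 1: the plan's own figures.**
- Effective size: 1,235 / (1 + 95 × 0.01) = 1,235 / 1.95 = 633.3, as stated. The usual design effect, 1 + 94 × 0.01 = 1.94, gives 636.6.
- 633 effective, 13% rising to 18.7%: power 79.4%, which reproduces the stated 80%.
- 633 effective, 13% falling to 7.3%, the direction the trial hopes for: d√n = 0.057 × 25.16 = 1.434; (1.434 − 1.96 × 0.4271) / 0.4252 = 1.40; power 92.0%.
- 633 enrolled (SAP): 633/13 = 48.7 per block; design effect 1 + 47.7 × 0.01 = 1.477; effective n = 428.6; power for 13% versus 7.3% is 79.0%, which also reproduces 80%.

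The stated 80% therefore has two readings. For a reduction, the starting power is 92% or 79%, so both are carried forward.

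**Step 2: dilution, if the 13% counts events at any time.** The relative reduction, 5.7/13 = 44%, acts only on post-surgery events.
- All events: 13% versus 13% − 5.7(1 − f) points.
- Post-surgery events only: 13(1 − f)% versus 7.3(1 − f)%.

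| f | All events | Post-surgery only | Power at 633 effective: all / post-surgery | Power at 428.6 effective: all / post-surgery |
|---|---|---|---|---|
| 0 | 13% v 7.30% | 13% v 7.30% | 92% / 92% | 79% / 79% |
| 10% | 13% v 7.87% | 11.70% v 6.57% | 85% / 89% | 69% / 74% |
| 25% | 13% v 8.73% | 9.75% v 5.48% | 69% / 82% | 52% / 66% |
| 40% | 13% v 9.58% | 7.80% v 4.38% | 49% / 72% | 35% / 55% |

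Example, last cell: d√n = 0.0342 × 20.70 = 0.708; (0.708 − 1.96 × 0.3382) / 0.3373 = 0.13; Φ = 55%.

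At 633 effective, power drops below 80% at f of about 15% with all events and about 28% with post-surgery events only. On the SAP reading it is already just under 80% at f = 0.

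**Step 3: what the rule recovers.** At 633 effective, the losses from 92% are 7, 23 and 43 points, and the rule gives back 4, 13 and 24. The remainder arises because fewer events are preventable, which no definition can restore.

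**Step 4: if the 13% already means post-surgery events.** Adding x points of earlier events to both arms at 633 effective gives 90% at x = 1, 85% at x = 3 and 81% at x = 5; power falls below 80% from about x = 5.4. At 428.6 effective, x = 3 gives 70%. For comparison, 3 added points make 3/16 = 19% of all events early; in Step 2, f = 20% gives 75% at 633 effective.

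**The case against.** The best reply is that the plan is less open than it looks and that the size is guesswork. Much of this stands.

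- A reader might infer that the whole composite lacks a time window. It does not: death has a start and the SAP sets an end. The gap is the start of the near-miss window. Death's own start, delivery, does still precede the end of surgery.
- A reader might infer that every early complication will count. The documents show only that it can. The ICU exclusion removes some intra-operative cases, and the criteria are strict: convulsions must be refractory or persistent, and transfusion must reach five units.
- A reader might take the SAP margin comment listing women "deceased before monitoring" as proof that early deaths are counted as outcomes. That comment concerns who belongs to the intervention periods, and such deaths could follow surgery.
- A reader might infer a false-positive risk. If early events are equally frequent in both block types, the effect is pulled toward the null.
- f is not in the documents, so no single power figure can be claimed.

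The objection also bears on the remedy. Controls have record review only, and a SAP margin comment anticipates missing control-period data. If onset is less well documented in control blocks, counting unknown onset as post-surgery would retain more early events among controls and favor monitoring. That risk needs a safeguard. It does not justify leaving the window open.

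**Conclusion.** The point holds as a gap in the outcome definition. Followed as written, the plan can count near-miss events that monitoring could not have influenced, and any such events balanced between block types dilute the effect. The direction is firm. The size rests on the assumed f, on the 13% covering events at any time, on a 44% relative reduction confined to post-surgery events, and on which reading of 633 applies.

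Under those assumptions, f of 10% to 40% costs about 7 to 43 points of power from 92%, or 10 to 44 points from 79%. The loss is smaller if the 13% already refers to post-surgery events. It would be wrong to conclude that the trial is underpowered on this account: at 633 effective and a fall to 7.3%, power stays above 80% until f reaches about 15%. Nor can it be said that onset times go uncollected, because the chart review form (Appendix 1) is not among the documents. The change is worth making because it is cheap and makes a null result easier to interpret.

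**What to change.** - Define the primary SMO as any Table 1 component with onset after the end of the cesarean and before discharge, for all eligible women in both block types. Everyone stays in the denominator, so intention to treat is preserved.
- Ensure that chart review records onset relative to the end of surgery, from the same chart sources in both arms and without sensor data.
- State which window the 13% refers to, and whether 633 is an effective or an enrolled number.
- Count unknown onset as post-surgery in the primary analysis and report its proportion by arm. Add one sensitivity analysis that treats unknown onset as pre-surgery and another that counts all SMOs regardless of onset.

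The cost is SAP wording and, if the form lacks it, one chart field. The event rate will be lower if the 13% includes earlier events, and some onset times will need judgement. Death's start would move from delivery to the end of surgery; deaths in theatre would remain in the any-time analysis and in the secondary mortality outcome.

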##### Secondary outcomes

- Maternal Mortality ratio: Number of maternal deaths per 100,000 livebirths

**Commented [BAA1]:** Consider livebirths for only women included in the trial? Or consider livebirths for all women at the hospital

NCT ID: 2019P000885

Document Date: September 26th 2021

- Case fatality rate for
  - Hemorrhage – deaths/total number of hemorrhage cases
  - Hypertensive disorders of pregnancy- deaths/total number of HDP cases
  - Sepsis - deaths/total number of sepsis cases

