Doctors will benefit from having easier and more timely access to physiologic data, reducing their work burden and improving their ability to more fully care for their patients. Postpartum women will have the direct benefit of increased physiologic monitoring. In some cases, this can be life-saving as developing complications may be averted from earlier intervention. In addition, I anticipate that wireless maternal monitoring will ultimately help reduce rates of maternal and newborn morbidity and mortality, particularly in resource-limited settings. The results of the proposed study will help establish the preliminary efficacy of this strategy for monitoring and how to improve implementation. Furthermore, understanding mobility in the postpartum period and the financial risks associated with childbirth and its recovery, may help us reduce these risks and improve recovery from cesarean deliveries. Both type of participants may feel good about contributing to research in this area.

Monitoring and Quality Assurance

Prior to conducting the study, the research assistants will receive training on how to use the data collection tool, as well as standard clinical research ethics (i.e., the online CITI course available through Massachusetts General Hospital [MGH]).

A member of the study staff will verify completion of data as entered into the chart review forms prior to data analysis. Missing or inconsistent data that can be verified with the participant's chart or interviewed clinician prior to discharge will be entered retrospectively. Data that cannot be verified with the participant or their chart will not be included in data analysis. All quality control measures will be performed on a weekly basis and as needed.

Qualitative data will be transcribed within 48 hours of data collection and then translated into English if need be.

The principal investigators shall provide oversight and review of study protocols throughout the study. Quality checks will be performed on a weekly basis by the principal and co-investigators to ensure accurate data collection.

The principal investigators will review all potential instances of privacy violations or other concerns within 24 hours and communicate any adverse events to the MUST and MGH IRBs within 10 days.

A Data and Safety Monitoring Board (DSMB) will be convened.

Our chosen DSMB will include the following

1. [name] – Former Chair Dept of OB/GYN Makerere University
2. [name] – Lecturer, Dept of Medicine, MUST

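### The secondary case fatality rates divide deaths by case counts that monitoring can itself change, so the arms can differ with identical deaths

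*SAP*

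**What the plan says.** The SAP (Exposure and Outcome Definitions, Secondary outcomes) lists three case fatality rates: "deaths/total number of hemorrhage cases", "deaths/total number of HDP cases" and "deaths/total number of sepsis cases". It gives no case definition and no time limit on diagnosis. It does not say whether the deaths counted are deaths from that cause or any deaths among those cases.

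The same section lists "Maternal Mortality ratio: Number of maternal deaths per 100,000 livebirths". An unresolved margin comment asks: "Consider livebirths for only women included in the trial? Or consider livebirths for all women at the hospital".

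The SAP's Aim 1 text (printed under Protocol Deviations) says that the "event rate for the primary and secondary outcomes will be calculated during the intervention and control time periods on all eligible women" in those periods. The mixed logistic model named there covers the primary outcome only. The between-arm test for secondary outcomes comes from the protocol (Biostatistical Analysis, Aim 1), which applies logistic regression with GEE to both primary and secondary outcomes. The SAP (Test size and confidence levels) sets two-sided 0.05 tests without multiplicity adjustment.

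Three protocol statements bear on the case counts. Its opening section links hemorrhage, pre-eclampsia/eclampsia and sepsis to abnormal vital signs. Study Procedures (steps 4 and 9, Table 1) provide for measuring such signs and alerting clinicians during intervention blocks. Potential Benefits states that "developing complications may be averted from earlier intervention".

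**The concern.** A case fatality rate is a comparison among women who have a diagnosis. If the intervention affects who gets the diagnosis, the women in the two denominators are no longer comparable, and allocation by block does not protect the comparison.

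Here the intervention can act in both directions. Closer measurement of blood pressure, pulse and temperature may bring more mild cases into the record, which lowers the rate and looks like better survival. Preventing complications removes cases, probably the milder ones, which raises the rate and looks like harm. Neither effect operates in control blocks. A reader of the trial report could therefore take a change in diagnosis for a change in survival, or see a real preventive benefit reported as a worse outcome.

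**Working it through.** The documents give no expected figure for any case fatality rate or for the mortality ratio, so there is no planned value to reproduce. The arm sizes do reproduce from Sample Size: 112 × 0.85 = 95.2, or about 95 women per block; 95 × 13 = 1,235 per arm. All eligible women in 13 blocks: 112 × 13 = 1,456.

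**1. Effect of the denominator alone.** Hold deaths equal and multiply the intervention-arm case count by k. The ratio of case fatality rates is 1/k. The values of k are assumptions; the documents give none.

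| Change in recorded cases | k | Ratio 1/k | Apparent change |
|---|---|---|---|
| 10% more | 1.10 | 0.91 | 9% lower |
| 25% more | 1.25 | 0.80 | 20% lower |
| 50% more | 1.50 | 0.67 | 33% lower |
| 20% fewer | 0.80 | 1.25 | 25% higher |

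Example: 3 deaths in 100 cases is 3.0%; 3 in 150 is 2.0%; 3 in 80 is 3.75%.

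Reversal is also possible. If deaths fall by 10% and cases by 20%, the ratio is 0.90/0.80 = 1.125, so fewer deaths appear as a rate 12.5% higher.

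**2. Dilution by earlier diagnoses.** If a share f of cases is known before monitoring, the effective multiplier is f + (1 − f)k. With f = 0.5 (assumed) and k = 1.5, it is 1.25, so the apparent reduction is 20% instead of 33%. With f = 0.8 it is 1.10, or 9%.

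**3. Expected deaths per arm.** Inputs: 460 per 100,000 (protocol, Setting) and shares of 27.1%, 14.0% and 10.7% (protocol, opening section). Applying a whole-hospital ratio and worldwide shares to emergency cesareans is an assumption.

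- All causes: 0.0046 × 1,235 = 5.7; 0.0046 × 1,456 = 6.7.
- Hemorrhage: 5.68 × 0.271 = 1.5; 6.70 × 0.271 = 1.8.
- Hypertensive disease: 0.8 to 0.9.
- Sepsis: 0.6 to 0.7.

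**4. Chance in the numerator.** Take two independent Poisson counts with the same mean, ignoring clustering. The counts differ between arms with probability 58% at a mean of 0.6 and 78% at 1.8. They differ by at least 1.5-fold (counting 0 against 1 or more) with probability 58% and 75%.

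**5. Livebirths.** The device is placed after surgery is complete (Study Procedures, step 6), so monitoring cannot change livebirth status. Chance imbalance in livebirths per woman is about ±1.96 × √(2p(1 − p)/n)/(1 − p). With n = 1,235 and an assumed stillbirth risk p of 3% to 10%, this is ±1.4% to ±2.6%. For whole-hospital livebirths, assumed at about 5,000 per arm (half of roughly 10,000 yearly deliveries), exp(1.96 × √(2/5,000)) = 1.04, or about 4%. The choice mainly sets the level: 6 deaths is 6/(1,235 × 0.95) = 511 per 100,000 on trial livebirths (5% stillbirth assumed), and 6/5,000 = 120 per 100,000 on hospital livebirths.

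**6. Deaths over all eligible women.** With 6 deaths in 1,456 women in each arm, both rates are 412 per 100,000 and the ratio is 1.00, whatever the number of diagnoses.

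**The case against.** The strongest reply is that the quantities are small and partly hypothetical. The detection and prevention percentages have no source in the documents. Some cases will be known before monitoring: Study Procedures step 12 extracts antenatal complications and the indication for cesarean, so many hypertensive cases may precede it. The outcomes are secondary. All of this stands and limits the size of the problem, but it does not remove the mechanism, because nothing in the SAP restricts the denominator to those earlier cases.

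Four stronger readings are tempting and are not supported.

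- A reader might infer that the mortality ratio is biased in the same way. It is not, because livebirths are fixed before monitoring begins.
- A reader might infer that the Aim 1 text flatly contradicts the Secondary outcomes section. That sentence follows a list of women who declined, were missed or were not enrolled, and can be read as fixing only the source population, within which a case fatality rate could be calculated. The two places are unreconciled, but a contradiction is not shown.
- A reader might infer that the denominator would account for most of any observed difference. With so few deaths per cause, step 4 shows that chance in the numerator would usually matter more.
- A reader might infer that the main result is compromised. The primary composite includes death, is analyzed on all eligible women, and does not use these denominators.

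**Conclusion.** The concern holds for the three case fatality rates. As planned, they are compared between arms over a count that the intervention can raise or lower, so the comparison can show a difference, or reverse one, without a matching change in deaths. The illustrative size is 9% to 33% lower for 10% to 50% more recorded cases, and 25% higher for 20% fewer. These shifts are assumed, and pre-monitoring diagnoses would shrink them. At about 0.6 to 1.8 expected deaths per cause per arm, under the assumptions in step 3, the comparisons carry almost no information even apart from this bias.

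For the mortality ratio the defect is one of definition: the livebirth population is undecided, and a ratio per livebirth is not a woman-level proportion of the kind the protocol's logistic model needs. The matter deserves correction before analysis but does not touch the primary conclusion.

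**What to change.** Amend the SAP's Secondary outcomes section and the protocol's Aim 1 analysis text together.

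- Make the compared mortality outcome all-cause deaths over all eligible women in the period, consistent with the population in the SAP's Aim 1 text.
- Add deaths attributed to hemorrhage, hypertensive disease and sepsis over the same denominator, where the chart gives a cause.
- Define a case for each condition and report case counts by arm.
- Report case fatality descriptively, without a between-arm test, or limit it to cases diagnosed before monitoring starts.
- Report the mortality ratio descriptively, on livebirths of the same eligible women, and close the margin comment.

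The cost is modest but goes beyond SAP wording. An outcome listed in the protocol becomes descriptive, so the protocol changes too. Cause of death must be assigned from the records; the items listed in Study Procedures steps 11 and 12 do not include it, and the chart review form is in an appendix not among the documents reviewed.
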